2.3.3.4 AE of Interests

Adverse events of interest additionally include the following categories from CRFs:

- Cerebrovascular Accident/Transient Ischemic Attack
- Coronary Ischemia
- Venous Thromboembolism

AE listing will be provided for each AESI category including the seriousness of the AE.

2.3.4 *Laboratory Measurements*

The following is the list of routine lab analytes that may be collected throughout the study:

- Chemistry: Total protein, Albumin, Glucose, Blood urea nitrogen (BUN) for urea reduction ratio (URR) determination, Total bilirubin, Direct bilirubin, Indirect bilirubin, ALT, AST, GGT
- Hematology: Red blood cells, Hemoglobin, Hematocrit, MCV, MCH, MCHC, Platelets, Mean Platelet Volume, WBC, and WBC differential (percentage and absolute) (Basophils, Eosinophils, Lymphocytes, Monocytes, and Neutrophils)
- Inflammatory Markers: Hs-CRP, D-climer, Beta-2-M, Cardiac troponin I and T, NT-proBNP
- Screening Tests: Hepatitis B surface antigen, Hepatitis C antibody, HIV antibody, FSH (women only, if applicable) and Serum PhCG (women only). This data will only be displayed in patient listings.

Missing WBC differential absolute counts and percentages will be derived as needed:

If WBC differential absolute counts are missing, and percentages are available, then absolute counts will be calculated by multiplying the percentage by total WBC count. Conversely, if absolute count is available, and percentage is missing, then percentage will be calculated by dividing absolute count by the total WBC count. If neutrophils counts and percentages are missing, and segmented neutrophil and band neutrophil results are available, then neutrophils will be calculated by adding segmented neutrophils and band neutrophils.

Chemistry and hematology panel results, change and percent change from baseline will be summarized by treatment group and study visit.

For ALT and AST, the number and percent of patients falling in each of the following categories for central laboratory data will be tabulated by treatment group:

- Confirmed ALT \geq 3x ULN
- Confirmed ALT \geq 5x ULN
- Confirmed AST \geq 3x ULN
- Confirmed AST \geq 5x ULN

A confirmed laboratory value is based on consecutive lab values within 7 days. If that value is in the same or worse category, then the initial value is confirmed. If the consecutive value is in a better category, then the initial value is confirmed using consecutive value category. If there is no retest within 7 days, the initial value is presumed confirmed. If there are multiple results on the same day (no matter from the same lab vendor or different lab vendors), then the worst value will be utilized in the analysis.

BCH flow cytometry data for platelet function will be summarized separately. The Versiti (Blood Centers of Wisconsin) data will be listed.

All patients meeting safety monitoring and stopping rules will be listed.

2.3.5 Vital Signs

Vital signs will include heart rate, respiratory rate, body temperature, and systolic and diastolic blood pressure. For continuous parameters scheduled to be measured in duplicate or triplicate, the mean will be presented in tables and figures.

Summary tables will be created to present the descriptive statistics for vital sign values as well as the change and percent change from baseline at each study visit.

2.3.6 Physical Examinations

Adverse changes in physical examinations that are deemed clinically significant by the Investigator will be classified as adverse events. All physical examination data will be provided in a data listing.

2.3.7 12-Lead Electrocardiograms (ECG)

The ECG data will include ventricular rate (VR), PR interval, QRS duration, QT, QTC (recorded from ECG machine).

Summary tables will be created to present the descriptive statistics for ECG parameters as well as the change and percent change from baseline at each study visits. For continuous parameters scheduled to be measured in duplicate or triplicate, the mean will be used for tables and figures.

For the categorical responses to overall interpretation, counts and percentages will be provided. If multiple results are available, the worst case result will be used in the summary.

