1.1 Study Overview

This is a Phase 2 multicenter, double-blind, randomized, stratified, placebo-controlled study in end-stage renal disease (ESRD) subjects receiving hemodialysis at least 3 times per week for a minimum of 9 hours per week. Subjects will be stratified based on the diagnosis of documented atrial fibrillation (AF) at Screening (Yes/No), enrolled in PK substudy (Yes/No), enrolled in Platelet substudy (Yes/No), and then subjects will be randomized to 1 of 3 dose cohorts in a 1:1:1 ratio (Cohort A, Cohort B, and Cohort C). Within each dose cohort, subjects will be randomized in a 3:1 ratio to receive treatment with Study Drug (either ISIS 416858 or placebo).

Cohort A: 200 mg ISIS 416858 or placebo SC (3:1)

Cohort B: 250 mg ISIS 416858 or placebo SC (3:1)

Cohort C: 300 mg ISIS 416858 or placebo SC (3:1)

All cohorts will consist of up to 4-week screening period for procedures and a 26-week treatment period followed by a 12-week post-treatment evaluation period.

Approximately 204 subjects are planned to be enrolled in parallel in this study.

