2 ANALYTICAL PLAN

2.1 General Overview of Analyses

2.1.1 General Statistical Methods

Descriptive summary statistics including number of patients, mean, standard deviation, median, and range (minimum, maximum) for continuous variables, and counts and percentages for categorical variables will be used to summarize most data. All statistical tests will be conducted using 2-sided tests with 5% Type I error rate unless otherwise stated.

PK parameters will be summarized using number of patients, mean, standard deviation, coefficient of variation (CV), geometric mean, median, minimum, and maximum.

All analyses and tabulations will be performed using SAS® Version 9.2 or higher and Phoenix/WinNonlin version 6.1 or higher on a PC platform.

A separate analysis for on-treatment period might be provided if deemed necessary.

Pooled groups:

Patients who are placebo-treated will be pooled and analyzed as a single placebo group.

Patients who are ISIS 416858-treated may be pooled and summarized as the ISIS 416858 total group.

Baseline definition:

Unless otherwise specified, baseline for all safety laboratory results will be defined as the last non-missing measurement prior to the first dose. For post-dialysis Blood Urea Nitrogen (BUN) measures for Urea Reduction Ratio (URR) determination, post-dialysis baseline will be defined as the last non-missing post-dialysis measurement prior to the first dose

Analytical visits:

All post-baseline data will be summarized according to the visit windows in the table below. For patients who have multiple visits within a window, the average will be used in the summary for continuous variable and the worst case result will be used for categorical variable.

Table I Visit window for Clotting

Analysis visit	Visit window
Screening	<1
Baseline	last non-missing measurement prior to the first dose
Day8	[2, 11]
Day 15	[12, 21]
Day29	(22, 35]
Day43	[36, 49]
Day 57	[50, 63]
Day71	[64, 77]
Day 85	[78, 91]
Day99	(92, 105]

Day 113	[106, 116)
Day 120	[117, 126)
Day 134	(127, 140)
Day 148	(141, 154)
Day 162	[155, 168)
Day 176	[169, 182]
Day 190	(183, 196]
Day 204	[197, 210]
Day 218	[211, 224]
Day 232	[225, 238]
Day 246	(239, 252]
Day 260	[253, 266]

Table 2 Visit window for Vital Signs

Analysis visit	Visit window
Baseline	last non-missing measurement prior to the first dose
Day 5	(2, 6)
Day 8	[7, 9]
Day 12	[10, 13]
Day 15	[14, 17]
Day 22	[18, 25)
Day 29	[26, 32)
Day 36	[33, 39)
Day 43	[40, 46]
Day 50	[47, 53]
Day 57	[54, 60]

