2.1.3 Sample Size Consideration

The sample size was selected based on prior experience to ensure that the safety, tolerability and PK/PD relationships will be adequately assessed while minimizing unnecessary patient exposure. There is no statistical rationale for the selected sample size.

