2.3 Safety Analyses

Safety analyses will be based on the safety population. Safety summary tables will be presented by treatment group and ISIS 416858 total.

2.3.1 *Exposure*

Treatment duration, time on study, number of doses and amount and total volume of Study Drug (ISIS 416858 or placebo) received will be summarized by treatment group and ISIS 416858 total.

The treatment duration (days) for each patient is defined as last dose date - first dose date +1.

The time on study will be defined as the total number of days a patient is known to be followed on study calculated as follows:

$$\text{Time on study} = \text{Last date on study} - \text{Date of first dose} + 1.$$

Where the last date on study is defined as the date of the latest visit with evaluation, or time of death from all available data for a given patient. Visits with refused or unable to contact are not visits with evaluation.

The amount of Study Drug received (mg) for each patient is defined as the total volume (mL) administered from the 200 mg/mL stock solution.

2.3.2 *Compliance*

Percentage of compliance will be calculated and summarized by treatment groups and ISIS 416858 total.

$$\text{Study drug compliance} = 100 \times (\text{Total number of doses with injections given} / \text{Total number of doses with injections expected}).$$

If a patient discontinued the study treatment, the total number of doses with injections expected is counted, per the schedule of injections, up to the last attended study visit during the treatment period.

2.3.3 *Adverse Events*

The treatment emergent adverse events (TEAE) are defined as those AEs that occurred after dosing and those existing pre-dose AEs that worsened post-dose during the study.

The most conservative approach will be used to determine if the event occurs during the treatment or follow-up periods:

- AEs that have onset dates or resolution dates prior to the first study treatment dates will be considered to have occurred prior to the study period. If the onset or resolution date

of an AE is a partial date with only month or year available or complete missing, then the event is assumed to be within the study period unless the year is prior to the year of the first study treatment date, or if in the same year, the month is prior to the month of the first study treatment date.

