3.2 Number of Study Centers

This study will be conducted at multiple centers worldwide.

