10.6.2 Safety Analysis

Treatment duration and amount of Study Drng (ISIS 416858 or placebo) received will be summarized by treatment group. Subject incidence rates of all AEs will be tabulated by the Medical Dictionary for Regulatory Activities (MedDRA™) system organ class, and by MedDRA™ term. Tables and/or narratives of treatment-emergent deaths, serious and significant AEs, including early withdrawals due to AEs, will also be provided.

All treatment-emergent AEs, all treatment-emergent AEs potentially related to Study Drng, all treatment-emergent serious AEs, and all treatment-emergent serious AEs potentially related to Study Drng (ISIS 416858 or placebo) will be summarized.

Laboratory tests to ensure subject safety including chemistly panel, complete blood count with differential, coagulation panel, complement etc., will be summarized by study visits for each treatment group. These safety variables will also be presented as change and percent change from Baseline over time after Study Drng (ISIS 416858 or placebo) administration, as appropriate.

Vital sign and ECG measures will be tabulated by treatment group. In addition, the number of subjects who experience abnormalities in clinical laboratory evaluations will be summarized by treatment group.

Incidence of bleeding events including the following will be tabulated by treatment:

- MB
- CRNMB
- Minor bleeding
- Combination of MB and CRNMB

Physical examination data will be provided in the data listing. Concomitant medications will be coded using World Health Organization (WHO) Drng dictionruy and summarized by treatment, ATC class and generic name.

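### SAP 2.3.7 summarizes the QTc recorded from the ECG machine with no defined correction formula; one QTcF derived from the recorded QT and ventricular rate would define it at almost no cost

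*Combined protocol and SAP*

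**What the plan says.** The ECG variables are set out in SAP 2.3.7: "The ECG data will include ventricular rate (VR), PR interval, QRS duration, QT, QTC (recorded from ECG machine". The same section gives the analysis: "Summary tables will be created to present the descriptive statistics for ECG parameters as well as the change and percent change from baseline", by visit. It adds that replicate continuous measurements are averaged, and that the overall interpretation is tabulated by category.

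SAP 2.3 fixes the grouping: "Safety summary tables will be presented by treatment group and ISIS 416858 total". Protocol 10.6.2 agrees: "Vital sign and ECG measures will be tabulated by treatment group". Neither table is split by site or device. Protocol 3.2 states: "This study will be conducted at multiple centers worldwide".

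Under SAP 2.1.1, several visits falling in one analysis window are averaged for continuous variables. The ECG windows in SAP Table 3 are wide; Day 176, for example, covers Days 127 to 217.

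SAP 1.3.1 lists ECG among the items reviewed for safety and tolerability, and SAP 1.6.1 includes it in ongoing safety review. I found no correction formula, common ECG device or central reading in either document.

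**The concern.** QTc is a derived quantity: QT adjusted for heart rate by a chosen formula. Here the choice is left to the machine and is not recorded in the plan, so a reader of the tables cannot tell which QTc is reported.

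Two things could follow:

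- If formulas differ between machines, absolute means and SDs include formula differences that have nothing to do with treatment.
- If some or all machines use Bazett, QTc moves with heart rate even where repolarization is unchanged. A heart-rate shift in one arm would then appear as a QTc shift, or offset a real one. This second problem does not need mixed formulas.

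The plan already collects QT and ventricular rate, so it holds everything needed to define the variable once for all tracings.

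**Working it through.** The documents give no QTc formula, SD, threshold or power figure, so there is no planned figure to reproduce. The formulas below are standard ones. The heart rates, QT values and SDs are assumptions chosen to show scale.

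Formulas, with RR = 60/VR in seconds and VR in bpm:

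- Bazett: QT / RR^(1/2)
- Fridericia: QT / RR^(1/3)
- Framingham: QT + 154 × (1 − RR)
- Hodges: QT + 1.75 × (VR − 60)

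**Step 1: absolute offset, Bazett against Fridericia.** Fix QTcF at 420 ms, so QT = 420 × RR^(1/3). Bazett then equals 420 × (VR/60)^(1/6).

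| VR (bpm) | QT (ms) | Fridericia | Bazett | Offset |
|---|---|---|---|---|
| 70 | 399.0 | 420 | 430.9 | 10.9 |
| 80 | 381.6 | 420 | 440.6 | 20.6 |
| 90 | 366.9 | 420 | 449.4 | 29.4 |

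**Step 2: spread across formulas for one tracing.** This step does not assume that any formula is true. With QT = 400 ms:

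| VR (bpm) | Bazett | Fridericia | Framingham | Hodges | Largest − smallest |
|---|---|---|---|---|---|
| 70 | 432.0 | 421.1 | 422.0 | 417.5 | 14.5 |
| 80 | 461.9 | 440.3 | 438.5 | 435.0 | 26.9 |
| 90 | 489.9 | 457.9 | 451.3 | 452.5 | 38.6 |

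Using one formula throughout makes this spread zero by construction.

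**Step 3: spurious change in one patient.** With QTcF held at 420 ms and heart rate rising from 70 to 75 bpm, the change is +5.0 ms under Bazett, −0.3 ms under Framingham and Hodges, and 0 under Fridericia. The last is zero only because Fridericia was taken as the true relation.

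**Step 4: effect on the planned summaries.** The simulation assumes baseline VR with mean 75 and SD 10, baseline QTcF with mean 420 and SD 20, SD of true QTcF change 15, and SD of VR change 8. Each patient stays on one formula, and Fridericia is true.

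| | All Fridericia | 50/50 mix | All Bazett |
|---|---|---|---|
| Baseline mean (ms) | 419.9 | 427.6 | 435.3 |
| Baseline SD (ms) | 20.0 | 22.8 | 22.9 |
| Mean change, no VR shift (ms) | 0.03 | −0.12 | −0.27 |
| SD of change (ms) | 15.0 | 16.2 | 17.4 |
| Mean change, VR up 5 bpm (ms) | 0.03 | 2.29 | 4.55 |

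The difference between an arm shifted by 5 bpm and an unshifted arm is 2.29 + 0.12 = 2.41 ms for the mix and 4.55 + 0.27 = 4.82 ms for all Bazett.

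**Step 5: scale against sampling error.** The SAP plans about 204 patients, in three cohorts of about 68 randomized 3:1. That is 68 × 3/4 = 51 per dose and 3 × 17 = 51 on pooled placebo. The standard error of a difference in mean change is SD × √(2/51) = SD × 0.198, which gives 2.97, 3.21 and 3.45 ms for the three columns. Under these assumed SDs, the loss of precision is small, and the spurious shift is of the order of one standard error.

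**The case against.** The strongest case against is that little depends on this variable. No QTc test or threshold category is planned, and the stopping rules in protocol 8.6.1 to 8.6.3 concern liver tests, platelets and bleeding. The primary safety outcome is major plus clinically relevant non-major bleeding. A constant formula offset largely cancels in change from baseline when a patient stays on one machine, and blinded randomization balances machines across arms on average. Heart rate and uncorrected QT are summarized too, so a heart-rate shift between arms would be visible. All of this stands, and it keeps the point minor. It does not supply a definition for a variable that the SAP tabulates.

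A reader might infer four stronger things that the documents do not support:

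- **That sites use machines with different formulas.** The SAP says only that QTc comes from the ECG machine, and the protocol says only that there are many centers. Uniform equipment is neither shown nor excluded.
- **That 11 to 29 ms is the error in the treatment comparison.** It is a cross-sectional gap between two formulas. The comparison of changes is affected far less, as Step 4 shows.
- **That a single formula removes heart-rate error.** It removes mixing. Bazett used throughout would keep the error, and Fridericia reduces it only as far as it fits this hemodialysis population, which the documents do not address.
- **That bleeding or anemia will shift heart rate in one arm.** This is worth guarding against, but nothing in the documents shows such a shift.

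**Conclusion.** The point holds as a minor, easily made improvement. The QTc tables rest on an undefined correction and may mix formulas, while the data needed to define it are already collected.

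The size depends on facts that the documents do not give. If Bazett is in use, absolute QTc is raised by about 11 to 29 ms at 70 to 90 bpm for a QTcF of 420 ms. Without a heart-rate difference between arms, mean change is nearly unaffected and its SD rises from 15.0 to 16.2 ms (half Bazett) or 17.4 ms (all Bazett). With an assumed 5 bpm rise in one arm, the spurious mean change is about 2 to 5 ms. These figures take Fridericia as the true relation and rest on the assumed rates and SDs. If every machine already applies Fridericia, nothing changes except that the plan says so.

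**What to change.** In SAP 2.3.7:

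- Derive QTcF = QT / (60/VR)^(1/3), with VR in bpm, for each tracing. Do this before averaging replicates or visits within a window, because the formula is nonlinear and the order affects the result.
- Use QTcF for the value, change and percent-change summaries. Keep the machine QTc in listings.
- Flag tracings in atrial fibrillation, or summarize them separately, because irregular RR intervals limit any correction. Atrial fibrillation is a stratification factor, so such patients are expected. If rhythm on the tracing is not captured, the atrial fibrillation population in SAP 2.1.2 can serve for the separate summary.
- Describe QTcF as reducing heart-rate error, not removing it.

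The cost is a few sentences, one derived variable and one flag. It needs no new data and adds no site burden.

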2.3.8 Concomitant Medications

Concomitant medications will be coded using WHO Drug dictionary Version Mar 2018 and summarized by ATC class, generic name and treatment group. Prior medications and Concomitant medications will be summarized by treatment group for the Safety population. Prior medications include medications started and stopped prior to study drug administration (Day 1). Concomitant medications include medications (1) started prior to, and continued after Day 1, or (2) medications started on or after Day 1.

All transfusions will be summarized and listed for all patients as recorded on the transfusion logCRF.

2.3.9 *Ancillary procedures*

Ancillary procedures will be provided in the listing.

2.3.10 *Changes in Dialysis Access*

Changes in dialysis access prescription will be listed.

2.4 Pharmacodynamic Analyses

The pharmacodynamic analysis will be conducted on the Per Protocol Population and will be presented according to treatment group and ISIS 416858 total. The baseline is defined as the latest- assessment prior to first dose of study drug.

Change and percent change from baseline FXI activity and antigen levels and aPTT will be summarized by treatment and visit separately. Individual results will be presented in data listings by treatment. Figures of the mean FXI activity and antigen levels and aPTT results as well as change and percent change from baseline will be provided by treatment group, and scheduled visit.

Change and percent change from baseline in FXI activity and antigen levels and aPTT will be compared between each of the ISJS-416858 treated group and pooled placebo group using the ANOVA or Wilcoxon Rank Sum test, as appropriate. The normality will be tested by applying Kolmogorov-Smirnov test on the residuals (difference between individual values and group mean). Numeric values will be rounded to 5 decimal places when applying Wilcoxon Rank Sum test or Kolmogorov-Smirnov test.

Frequency and percent of patients with average FXI activity .1, -2, s>.3, ..., :9.0U/mL during Day 50 to Day 176 (inclusive) up to last dose+ 7 days will also be provided.

The incidence and events for any aPTT>160s will be summarized by treatment and visit.

The clotting assessment will be conducted on the Per Protocol Population and will be presented according to treatment group and ISIS 416858 total.

The clotting assessment will consist of a quantitative scale by descriptive category (see details in table 1) and will be performed by trained personnel.

Table 1 Clotting Scale

Inspection site	Category 1	Category 2	Category 3	Category4
Air Trap	No clotting	Fibrinous ring with no clot formation on venous chamber filter	Clot formation on venous chamber	Coagulated system (treatment cannot continue without new setup)
Dialyzer	Clean dialyzer	Blood stripes affecting less than 5% of the fibers seen at the surface of the dialyzer	Blood stripes affecting 5% or more of the fibers seen at the surface of the dialyzer	Coagulated filter

Overall score is the highest of the individual component scores

Individual Category Summary

The frequency and percentage of patients in each clotting category will be summarized by inspection site (air trap, dialyzer) for each visit including screening visit. The overall score for individual clotting category, which is the highest of the inspection site Air Trap and Dialyzer score, will also be summarized.

In addition, the frequency and percentage of patients for overall score in each clotting category will be summarized by the following visits:

Week 26 or ET results for patients completed Week 8.

The denominator is the number of patients with at least one non-missing clotting assessment for each specific period above. The overall score for individual clotting category (1, 2, 3, or 4) will be analyzed for treatment comparison between each of the ISIS-416858 Treated group and placebo group using the Wilcoxon Rank Sum test.

In addition, the overall score for individual clotting category (1, 2, 3, or 4) will be analyzed using the proportional odds model with treatment as main effect. The proportional odds model with treatment as main effect and baseline clotting category as covariate will also be provided. P-value, odds ratio, and 95% confidence interval will be provided.

At least one clotting category ≥ 3

The frequency and percentage of patients with at least one post-baseline clotting category 3 or greater event after Week 8 (Day 50) and up to last dose + 7 days will be summarized by treatment group for each of the following periods for subjects on treatment:

- Before Week 8
- After Week 8 and up to last dose + 7 days

The denominator is the number of patients with at least one non-missing clotting assessment after Week 8 and up to last dose+ 7 days. The corresponding Ex.act Binomial 95% confidence interval will be provided.

A logistic regression model with treatment as main effect will be used to test the treatment difference between ISIS 416858 versus placebo in the proportion of patients with at least one clotting category 3 or greater. An estimate of the odds ratio, p-value and two-sided 95% confidence interval will be computed from the model using Wald's test. The logistic regression model with treatment as main effect and baseline clotting category as covariate will also be provided.

In addition, the number of events across all subjects of dialysis circuit will be summarized by treatment group.

Patient percentage of events greater or equal to 3 will be summarized for 2 periods (before Week 8, after Week 8 and up to last dose+ 7 days). The change of the percentages will be summarized and analyzed by ANOVA.

Most severe clotting category

In order to examine the correlation of FXI activity level and clotting, a separate summary on the most severe clotting category will be provided for patients with average Pre-dialysis FXI activity :::{.1}, :::{.2}, :::{.3}, ... , :::{1.0} U/mL during Week 8 and Week 26 (Day 176) (inclusive) for ISIS 416858 treated patients only.

Additional summary for frequency and percent of events with ≥ 3 clotting category with average Pre-dialysis FXI activity :::{0.1}, :::{.2}, :::{.3}, ... , :::{1.0} U/mL during Week 8 and Week 26 (Day 176) (inclusive) will also be provided.

